### **5.1.3 Post-Treatment Period**

All subjects who receive at least one dose of the study drug will enter into the Post-Treatment Period. The Post-Treatment will begin the day following the last dose of study drug treatment and continue through Week 144 as outlined in [Appendix C](#). Subjects who prematurely discontinue during the Post-Treatment Period should return to the site for a discontinuation visit and undergo the study procedures as outlined in [Appendix C](#).

Subjects may also return to the site for an unscheduled study visit for additional safety assessments if the investigator or sponsor feels it is necessary.

The Post Treatment Period will assess safety, antiviral response, and growth and development.

Growth and development will be assessed using BMI, weight z score, height z score, and growth rate at Post-Treatment Weeks 12, 48, 96, 144. Growth rate is defined as the change in height over change in age from the previous visit.

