### **8.1.1 Demographics**

Demographics and baseline characteristics will be summarized by age group and overall. As a sensitivity analysis, subjects who receive a dose lower than the final dose chosen for the subject's age group might be summarized separately. The baseline value refers to the last non-missing measurement collected before the first dose of study drug is received in Part 1 or Part 2. Demographics include age, birth year, weight, height, body mass index (BMI), BMI z score (BMI z score will be calculated using WHO published BMI-for-age

z-score tables), weight and height z scores (weight and height z scores will be calculated using WHO published weight-for-age z-score and height-for-age z-score tables), gender, race ethnicity, geographic region and country. Baseline characteristics will include HCV genotype, prior HCV treatment history if applicable, baseline platelets ( $< 90$  or  $\geq 90 \times 10^9/L$ ), baseline albumin ( $< 35$  or  $\geq 35$  g/L), baseline alpha fetoprotein ( $< 20$  or  $\geq 20$  ng/mL), baseline HCV RNA levels (continuous) and ( $< 1,000,000$ ,  $\geq 1,000,000$  to  $< 2,000,000$ ,  $\geq 2,000,000$  IU/mL), baseline fibrosis stage (F0-1, F2, F3, F4), baseline Fibrotest score, baseline APRI, and baseline Child-Pugh score (non-cirrhotic, 5 or 6).

Descriptive statistics will be provided, such as the number of observations (N), mean, and standard deviation (SD) for continuous variables (e.g., age, weight and height z-score) and counts and percentages for discrete variables (e.g., gender and race).

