6.2 Definition of Analysis Windows

For efficacy analyses of HCV RNA and resistance, the time windows specified in [Table 3](#) and [Table 4](#) describe how HCV RNA and resistance data are assigned to protocol-specified time points during the Treatment and PT Periods, respectively. All time points and corresponding time windows are defined based on the date/time of blood sample collection.

For safety laboratory data, vital signs, and growth and development endpoints (except growth rate), the time windows specified in [Table 3](#) and [Table 5](#) describes how data are assigned to protocol specified time points. For the calculation of growth rate only, the time window specified in [Table 6](#) will be used to assign height to a specific visit window before growth rate will be calculated as the change in height over change in age from the previous visit at Post-Treatment Weeks 12, 48, 96, and 144.

For PRO questionnaire, the time windows specified in [Table 7](#) and [Table 8](#) describes how data are assigned to protocol specified time points.

For palatability questionnaire, the time windows specified in [Table 9](#) describes how data are assigned to protocol specified time points during the treatment period.

For longitudinal Fibrotest and APRI, the time windows specified in [Table 10](#) describes how data are assigned to protocol specified time points during the Post-Treatment period.

If more than one assessment is included in a time window, the assessment closest (except in analyses of SVR) to the nominal time will be used. If there are two observations equally distant to the nominal time, the latest one will be used in analyses. For analyses of SVR (e.g., SVR₁₂), the last value in the window will be used.

If multiple measurements are made on the same day for a safety laboratory parameter, a vital sign parameter, or a growth and development endpoint, the average of the values will be used to calculate descriptive statistics and in analyses of the mean change from baseline.

Table 3. Analysis Time Windows for HCV RNA, Resistance Endpoints, Laboratory, Vital Sign Measurements, Growth and Development Endpoints (Treatment Period)

Scheduled Visit	Nominal Day (Study Day)	Time Window (Study Day Range)
Day 1/Baseline ^a	1	≤ 1 ^a
Week 2	14	2 to 21
Week 4	28	22 to 42
Week 8	56	43 to 70
Week 12 ^b	84	71 to 98
Week 16 ^c	112	99 to 126
Final Treatment Visit ^d	2 to ≤ 2 days after last dose of study drug	

a. Day of first dose of study drug.

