Note: The result closest to the scheduled time point will be used. Data must also have Study Drug End Day > 2. Vital signs and growth and development endpoints are collected at every PT visit; hematology, chemistry, urinalysis, and coagulation panels are collected at Post-Treatment Week 4 and PTDC (if subject discontinued prior to Post-Treatment Week 4). For subjects with compensated cirrhosis at baseline, chemistry and coagulation panels are collected to calculate the Child Pugh Score.

Table 6. Visit Windows for Growth Rate Calculation (Post-Treatment Period)

Scheduled Time	Nominal Day (Study Drug End Day)	Time Window (Study Drug End Days Range)
Post-Treatment Week 12	84	3 to 210
Post-Treatment Week 48	336	211 to 504
Post-Treatment Week 96	672	505 to 840
Post-Treatment Week 144	1,008	841 to 1,999
Final Post-Treatment Visit ^a	> 2 days after the last dose of study drug	

a. The last value within the Post-Treatment Period window will be used to define the final post-treatment value. The lower bound of this Final window is Study Drug End Day 3.

Note: The result closest to the scheduled time point will be used. Data must also have Study Drug End Day > 2. For the calculation of growth rate only, height will be assigned to a visit as described in the table above, then growth rate will be calculated as the change in height (millimeter) over the change in age (years) from the previous visit. If height is missing at a visit and/or the previous visit, then growth rate will be missing for the visit.

Table 7. Analysis Time Windows for PRO Instruments (Treatment Period)

Scheduled Visit	Nominal Day (Study Day)	Time Window (Study Day Range)
Day 1/Baseline ^a	1	≤ 1 ^a
Week 8 ^b	56	2 to 70
Week 12 ^c	84	71 to 98
Week 16 ^d	112	99 to 126
Final Treatment Visit ^e	2 to ≤ 2 days after last dose of study drug	

- a. Day of first dose of study drug.
- b. For 8-week treatment only.
- c. For 12-week treatment only.
- d. For 16-week treatment only.
- e. The last value within the window will be used to define the Final Treatment Visit value. The upper bound of this Final window is Study Drug End Day ≤ 2.

Note: Data must also have Study Drug End Day ≤ 2 for all windows. The result closest to the scheduled time point will be used. PRO instruments are collected at Day 1 and End of Treatment Visit, which can be at Weeks 8, 12 or 16 depending on treatment assignment.

Table 8. Analysis Time Windows for PRO Instruments (Post-Treatment Period)

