10.9 Growth and Development

The following growth and development endpoints will be calculated in the ITT population.

- Growth rate at Post-Treatment Weeks 12, 48, 96 and 144 (defined as change in height over change in age from the previous visit)
- Weight z score⁵
- Height z score⁵
- Body mass index (BMI) z score⁵

Weight, height, and BMI z scores will be calculated using WHO published weight-for-age z score, height-for-age z score, and BMI-for-age z score tables, respectively. As described in Section 7.1, subjects who are older than 10 years at the time of the corresponding weight measurement will be excluded from the analyses of weight z score. If a subject becomes older than 19 years during the study, the WHO standards at 19 years old will be used to calculate height z score and BMI z score after 19 years old as these WHO standards are very close to the adult standards.

Growth rate will be summarized with N, mean and SD together, median and range together at each applicable post baseline visit by gender for all and for age group separately. Weight, height and BMI z scores will be summarized with N, mean and SD together, median and range together at each applicable post baseline visit for all and by age group.

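### SAP Table 6 gives the planned PT Week 12 growth rate no previous visit, so the one growth rate that could include the treatment period has no defined starting height

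*SAP*

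**What the plan says.** SAP 10.9 lists the endpoint as "Growth rate at Post-Treatment Weeks 12, 48, 96 and 144 (defined as change in height over change in age from the previous visit"). Protocol 5.1.3 agrees: "Growth rate is defined as the change in height over change in age from the previous visit". Neither says which visit precedes PT Week 12.

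SAP 6.2 then sets up the derivation:

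- Tables 3 and 5 serve laboratory data, vital signs and "growth and development endpoints (except growth rate), the time windows specified in" those tables. Table 3 holds the Day 1 and on-treatment windows, so growth rate is cut off from them.
- The note to Table 6 says: "For the calculation of growth rate only, height will be assigned to a visit as described in the table above".
- The first row of Table 6 reads "Post-Treatment Week 12 84 3 to 210": nominal day 84, window 3 to 210, counted from the last dose. The remaining dated rows are PT Weeks 48, 96 and 144.
- The same note requires: "Data must also have Study Drug End Day > 2".
- It closes with the missing-data rule: "If height is missing at a visit and/or the previous visit, then growth rate will be missing for the visit".

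**The concern.** The PT Week 12 rate is planned in both documents, yet the rules for computing it supply no earlier height. Taken as written, they leave that column of the growth-rate table blank. If a programmer fills the gap, the result depends on an unstated choice between starting points that measure different things.

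The gap falls at the one time point where it matters. The participants are children from 3 years of age, and the other three growth rates begin after dosing has ended. A growth rate that reflects any of the 8 to 16 weeks of treatment can come only from PT Week 12.

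**Working it through.** The plan states no figure to reproduce. The check is to place every scheduled height into Table 6 and apply the rules in order.

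**Inputs.** Height visits come from Protocol Appendix C: Day 1, the on-treatment visits, end of treatment (EOT), and PT Weeks 4, 12, 24, 36, 48, 96 and 144. Windows and nominal days come from SAP Table 6. By SAP 6.1.2 the last dosing day is Study Drug End Day 0, so Day 1 is End Day −(7 × weeks of treatment − 1): −55, −83 or −111 for 8, 12 or 16 weeks.

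**Step 1: assign heights.**

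| Scheduled height | Study Drug End Day | Table 6 window |
|---|---|---|
| Day 1 to EOT | −111 to 0 (from −55 or −83 for 8 or 12 weeks) | none |
| PT Week 4 | 28 | PT Week 12 |
| PT Week 12 | 84 | PT Week 12 |
| PT Week 24 | 168 | PT Week 12 |
| PT Week 36 | 252 | PT Week 48 |
| PT Week 48 | 336 | PT Week 48 |
| PT Week 96 | 672 | PT Week 96 |
| PT Week 144 | 1,008 | PT Week 144 |

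The PT Week 4 height falls in the same window as PT Week 12, so it is not a separate visit in Table 6. The height closest to the nominal day is kept, which for a child on schedule is day 84.

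**Step 2: take differences.**

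- PT Week 12: no earlier row, so no interval. The missing rule leaves it empty for all three treatment durations.
- PT Week 48: 336 − 84 = 252 days.
- PT Week 96: 672 − 336 = 336 days.
- PT Week 144: 1,008 − 672 = 336 days.

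The last three all start after the last dose.

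**Step 3: compare the starting points a programmer might choose for PT Week 12.** Interval = 84 − starting End Day. On-drug share = days from Day 1 to last dose ÷ interval.

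| Starting height | Interval (days) | On-drug share |
|---|---|---|
| PT Week 4 | 84 − 28 = 56 | 0 |
| EOT | 84 − 0 = 84 | 0 |
| Day 1, 8 weeks | 84 + 55 = 139 | 55/139 = 40% |
| Day 1, 12 weeks | 84 + 83 = 167 | 83/167 = 50% |
| Day 1, 16 weeks | 84 + 111 = 195 | 111/195 = 57% |

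Of the three, only Day 1 brings any dosing time into the rate.

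**The case against.** The best defence is that baseline is obviously meant. SAP 6.1.1 says one baseline value serves both study periods. Other post-treatment tables (5, 8 and 10) also lack a baseline row and also admit only post-treatment data, yet change from baseline is planned for the endpoints they serve. An empty PT Week 12 rate would defeat an endpoint that both documents schedule, and Day 1 height is measured in every child.

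Much of this stands. A reader might infer that the PT Week 12 rate will be missing for every child. That is the literal result, not a forecast, since an analyst may well use baseline. But the defence does not supply the missing definition. The other endpoints are expressed as change from baseline, whereas growth rate is expressed as change from the previous visit. Nothing, including SAP 6.1.1, says that baseline is that visit. Protocol 5.1.3 read with Appendix C would point to PT Week 4 instead.

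Three other strong inferences fail:

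- *No growth over exposure is reported.* Height change from baseline is summarised at each visit (Protocol 8.1.3 and 8.1.5.3; SAP 11.4), and height z scores are summarised by visit (SAP 10.9).
- *Age is in whole years, so the divisor would be 0 or 1.* Protocol 8.1.1 says "Demographics include age, birth year, weight, height, body mass index (BMI"), but that is a list of summaries, not a rule on precision. SAP 7.1 treats age as continuous and applies its cut-off at 10 years at the time of each weight measurement. The Table 6 note gives a unit, not a rounding rule.
- *The rate would be swamped by measurement error over 8 weeks.* The documents give no error SD for height. That reading also needs PT Week 4 as a separate visit, which Table 6 does not allow.

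**Conclusion.** The gap is real and goes beyond missing detail. The PT Week 12 growth rate is planned, but the rules that derive it exclude every height that could come before it. On the literal text the rate is empty. In practice it would rest on an unstated choice between intervals of 56, 84, or 139 to 195 days, and only the last of these includes treatment (about 40% to 57% of the interval). These figures assume visits on their nominal days and full-length treatment.

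The consequence is limited. Growth rate is a descriptive summary and is not among the stated primary or secondary objectives, and the other height summaries still span exposure. They are not full substitutes. SAP 11.4.2 does not divide height change by elapsed time or split it by sex, as growth rate does, and SAP 12.1 item 4 removed change from baseline in the z scores. The point deserves correction before programming, but it does not threaten the trial's main conclusions.

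**What to change.** In SAP Table 6:

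1. Add a Baseline (Day 1) row.
2. Exempt that row from the condition on Study Drug End Day.
3. State that it is the previous visit for PT Week 12.
4. Define change in age as the days between the two height measurements divided by 365.25.

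The cost is one table row and a few sentences, with no new visit or measurement, because Appendix C already schedules a Day 1 height.

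The downside is that the first interval varies with treatment duration (139, 167 or 195 days, about 20, 24 or 28 weeks) and mixes on-treatment with post-treatment time. Dividing by elapsed time puts the rates on one annual scale but does not remove the mixture, so a footnote to the growth-rate table should say so.

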**Table 6. Treatment Regimen and Duration (Subjects in Japan)**

Patient Population	Duration
GT1 – 2 NC, TN, TE – IFN	8 weeks
GT1 – 2 C, TN, TE – IFN GT3 – 6 NC, C, TN, TE – IFN GT1 – 6 TE – SOF	12 weeks

Legend: C = Cirrhotic; NC = Non-Cirrhotic; TE – IFN = Japan Treatment experienced to IFN (alpha, beta or pegIFN) ± RBV; TE – SOF = Japan Treatment experienced to SOF/RBV; TN = Treatment Naïve

GLE/PIB will be administered as described in Section 5.5.1 (Treatments Administered). Subjects and their parent(s)/guardian(s) will receive instructions about the study drugs at the Day 1 Visit. The study drugs will be dispensed at the visits as indicated in [Appendix C](#).

After the Day 1 visit, all subjects will continue to return to the site on an outpatient basis for the study visits and procedures as identified in [Appendix C](#). Subjects could also return to the site for an unscheduled study visit for additional safety assessments if the investigator or sponsor feels it is necessary. Sites should ensure that subjects adhere to the study visits listed in [Appendix C](#). Subjects who cannot complete their study visit per the visit schedule should ensure they do not run out of study drug prior to their next study

visit. Study drug compliance is critical to ensure adequate drug exposure and optimal treatment outcome.

Virologic failure criteria will be evaluated and applied by the Investigator as detailed in Section 5.4.1.1.

Subjects who prematurely discontinue from the Treatment Period should return for a Treatment Discontinuation Visit and undergo the study procedures as outlined in [Appendix C](#) and as described in Section 5.5.1. Ideally, this should occur on the day of study drug discontinuation, but is recommended to be no later than 2 days after their final dose of study drug and prior to the initiation of any other anti-HCV therapy if applicable. Following completion or premature discontinuation of study drug treatment, all subjects in either Part 1 or Part 2 will be followed in the associated Post-Treatment Period of Part 1 or Part 2.

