- k. Perform a Fibrotest and APRI at Day 1 for any subject who did not have a FibroTest and APRI done during Screening.
- l. Applies only to subjects with cirrhosis. The Child-Pugh score will be calculated in the EDC RAVE system. Subjects who were considered to be non-cirrhotic at the Screening visit but identified as cirrhotic (according to definitions listed in Section 5.3.1.1) during the screening period will return to the site prior to the baseline visit for Child-Pugh assessment.
- m. HCC assessment for subjects with compensated cirrhosis only: Liver ultrasound will be performed at the screening visit. Subjects with a historical negative liver ultrasound, CT or MRI (within 3 months prior to screening) are not required to undergo a screening ultrasound.
- n. See specific information regarding the adverse event collection in Section 6.1.1.1.
- o. Study drugs are dispensed at Week 8 for subjects on 12 weeks of treatment and at Weeks 8 and 12 for subjects on 16 weeks of treatment.
- p. Dosing card is filled out with date and time (to the nearest minutes) of the 2 doses before PK draws in Part 1 and Part 2. Dosing cards should not be dispensed at Weeks 8 or 12 if those are EOT visits for the subject (Section 5.3.1.1).
- q. Intensive PK sampling will be done at Week 2 for the first approximately 12 subjects in each of the age groups and subjects in Japan participating in J-IPK (Section 5.3.2.1). Intensive PK samples will be collected at Week 2 visit at time points zero (0) and after two (2), four (4), six (6) and twelve (12) hours of drug intake. For subjects in Japan who will not participate in the J-IPK schedule, samples will be collected at Week 2 visit at time points zero (0) and after two (2) and four (4) hours of drug intake.
- r. Only applicable for HCV/HIV-1 co-infected subject.
- s. The Subject will retain the subject number throughout the course of the study.
- t. Resistance sample will be collected at Day 1. For a subject who meets virologic failure criteria, a resistance sample must be drawn at the confirmatory visit. If HCV RNA is < 1000 IU/mL in the sample collected at the confirmatory visit, another resistance sample will be collected in the following visit to ensure the HCV RNA is  $\geq$  1000 IU/mL.
- u. The PRO should be administered as the first study procedure.
- v. Only subjects in Part 2 will complete the palatability questionnaire, at Week 2 and EOT or premature discontinuation visit.

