6.1.2 Study Days

Study days are calculated for each time point relative to the first dose of study drug. Study days are negative values when the time point of interest is prior to the first study drug dose day. Study days are positive values when the time point of interest is after the first study drug dose day. There is no Study Day 0. Study Day 1 is the day of the first dose of study drug.

Study Drug End Days (Days Relative to the Last Dose of Study Drug)

Study drug end days are calculated for each time point relative to the last dose of study drug. The last day of study drug dosing is defined as Study Drug End Day 0. Days before it have negative study drug end days and days after it have positive study drug end days.

Final Treatment Value

The final treatment value is defined as the last non-missing measurement collected after Study Day 1 and on or before Study Drug End Day 2.

Final Post-Treatment Value

The final post-treatment value for each subject is the last non-missing measurement collected after Study Drug End Day 2 and on or before Study Drug End Day 1,999.

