Scheduled Time	Nominal Day (Study Drug End Day)	Time Window (Study Drug End Days Range)
Post-Treatment Week 12	84	3 to 1,999
Final Post-Treatment Visit ^a	> 2 days after the last dose of study drug	

- a. The last value within the Post-Treatment Period window will be used to define the final post-treatment value. The lower bound of this Final window is Study Drug End Day 3.

Note: The result closest to the scheduled time point will be used. Data must also have Study Drug End Day > 2.

Table 9. Analysis Time Windows for Palatability Questionnaire (Treatment Period Only)

Scheduled Visit	Nominal Day (Study Day)	Time Window (Study Day Range)
Week 2	14	2 to 35
Week 8 ^a	56	36 to 70
Week 12 ^b	84	71 to 98
Week 16 ^c	112	99 to 126
Final Treatment Visit ^d	2 to ≤ 2 days after last dose of study drug	

- a. For 8-week treatment only.
 b. For 12-week treatment only.
 c. For 16-week treatment only.
 d. The last value within the window will be used to define the Final Treatment Visit value. The upper bound of this Final window is Study Drug End Day ≤ 2.

Note: Data must also have Study Drug End Day ≤ 2 for all windows. The result closest to the scheduled time point will be used. Palatability questionnaire are administered to subjects in Part 2 at Week 2 and End of Treatment Visit or premature discontinuation visit.

Table 10. Analysis Time Windows for Longitudinal Fibrotest and APRI (Post-Treatment Period)

Scheduled Visit	Nominal Day (Study Drug End Day)	Time Window (Study Drug End Day Range)
Post-Treatment Week 12	84	3 to 175
Post-Treatment Week 48	336	176 to 504
Post-Treatment Week 96	672	505 to 840
Post-Treatment Week 144	1,008	841 to 1,999
Final Post-Treatment Visit ^a	> 2 days after the last dose of study drug	

Note: The result closest to the scheduled time point will be used. Data must also have Study Drug End Day > 2 for all windows. Study Drug End Day 0 is defined as the day of the last dose of study drug.

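### SAP Table 9 leaves out palatability forms completed 3 or more days after the last dose, so its Final Treatment Visit row can report the Week 2 answer

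*SAP*

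**What the plan says.** Protocol Appendix C (Treatment Period, note v) sets two occasions: "Only subjects in Part 2 will complete the palatability questionnaire, at Week 2 and EOT or premature discontinuation visit". Palatability is a secondary endpoint in Protocol 8.1.2.2 and SAP 10.4.2, summarised question by question at each applicable treatment visit, by age group and overall, with a by-subject listing.

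SAP 6.1.2 fixes the day scale ("The last day of study drug dosing is defined as Study Drug End Day 0") and the general rule: "The final treatment value is defined as the last non-missing measurement collected after Study Day 1 and on or before Study Drug End Day 2". SAP 6.2, Table 9, is titled "Analysis Time Windows for Palatability Questionnaire (Treatment Period Only"). Its note adds "Data must also have Study Drug End Day ≤ 2 for all windows", and footnote d says "The last value within the window will be used to define the Final Treatment Visit value". There is no post-treatment table for palatability.

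PedsQL follows the same cut-off in Table 7. It also has Table 8, which accepts any form from End Day 3 to 1,999 as Post-Treatment Week 12 (closest to Day 84) and takes the last one as the Final Post-Treatment value.

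On visit timing, Protocol 5.1.2 says the early-stop visit "is recommended to be no later than 2 days after their final dose of study drug". Protocol 5.4.1 gives the same 2 days in firmer terms, as a limit. Neither section, nor Appendix C, gives a day window for the EOT visit of a child who completes treatment.

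**The concern.** A 2-day cut-off suits HCV RNA, laboratory values and vital signs, where the question is whether drug was still acting. In those cases a later value moves into a post-treatment window that opens on End Day 3. A palatability form asks what giving the medicine was like, and the answer does not stop being about treatment on the third day. Because palatability has no post-treatment window, a late form leaves the windowed summaries altogether.

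The missing Week 8/12/16 entry is at least visible as a smaller denominator. The Final Treatment Visit row is the more serious problem: it would silently carry the Week 2 answer forward under an end-of-treatment label.

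PedsQL has a smaller, related problem. A late EOT form can be reported as a post-treatment score.

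**Working it through.** The plan gives no visit-timing figure to reproduce, so the check applies the tables literally to example records.

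**Inputs.**
- End Day = Study Day of visit − Study Day of last dose (SAP 6.1.2).
- Table 9 ranges: Week 2, Days 2–35 (nominal 14); Week 8, Days 36–70 (56); Week 12, Days 71–98 (84); Week 16, Days 99–126 (112). The last three each apply to one assigned duration only.
- Within a window the value closest to nominal is used. Final Treatment Visit is the last value with End Day ≤ 2.
- Tables 7 and 8 for PedsQL are as described above. On treatment, PedsQL is collected only at Day 1 and EOT or premature discontinuation.

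**Step 1: the note against the printed ranges.** The ranges extend past nominal by 70 − 56 = 14, 98 − 84 = 14 and 126 − 112 = 14 days. If dosing ends on the nominal day, the note ends use at Day 58, 86 or 114. The remaining days can never supply a value:

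| Window | Unusable days | Share of the Table 9 range |
|---|---|---|
| Week 8 | 59–70 | 12 of 35 |
| Week 12 | 87–98 | 12 of 28 |
| Week 16 | 115–126 | 12 of 28 |

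**Step 2: 8-week completer, last dose Day 56, Week 2 form on Day 14.**

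| EOT visit | End Day | Week 8 palatability | Final Treatment palatability |
|---|---|---|---|
| Day 56, 57 or 58 | 0, 1 or 2 | EOT answer | EOT answer |
| Day 59, 61 or 63 | 3, 5 or 7 | missing | Day 14 answer |

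With no Week 2 form and EOT on Day 60 (60 − 56 = End Day 4), both entries are missing.

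**Step 3: early stoppers.**
- Last dose Day 30, visit Day 32 (End Day 2): Final is the discontinuation answer.
- Last dose Day 30, visit Day 35 (End Day 5): Final is the Day 14 answer.
- Last dose Day 7, visit Day 12 (End Day 5), no other form: Final is missing.

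**Step 4: PedsQL, EOT on Day 61 (End Day 5).** Week 8 and Final Treatment are missing in either case.
- If a form exists at End Day 84, its distance from nominal is 0 against 84 − 5 = 79. The late EOT form is then used nowhere.
- If there is no later form, the End Day 5 form becomes both Post-Treatment Week 12 and Final Post-Treatment. SAP 10.10 reports change from baseline to the Final Post-Treatment Visit.

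**Step 5: weight of one record.** Protocol 5.5.3 aims for about 22 children per Part 2 age group on the final dose. One substituted answer moves a category by 1/22 = 4.5 percentage points.

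**The case against.** The strongest defence is that the cut-off agrees with the protocol. The protocol's definition of terms ends the Treatment Period at the last dose, so End Day 2 is already a grace period. For early stoppers, Protocol 5.4.1 sets the same 2 days. Protocol 5.1.2 also tells families who cannot keep the visit schedule not to run out of drug before the next visit, which tends to keep last dose and visit together. A by-subject listing is planned, reasons for stopping study drug are summarised separately (SAP 8.1), and nothing here touches AUC, SVR or any hypothesis test.

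Much of this stands. For early stoppers the SAP and protocol agree in substance, and only visits outside the protocol's own timing are affected. A reader who sees only the softer wording of 5.1.2 might infer that the SAP imposes a limit the protocol does not have; 5.4.1 shows otherwise. The defence does not cover completers, for whom no EOT window is stated. Nor does it explain why Table 9 prints ranges that its own note makes unusable. The listing may still show a late form, but it does not correct a summary row that shows a Week 2 answer as final.

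It is also fair that PedsQL differs from palatability. For a quality-of-life measure, being on or off drug matters, and counting a form from up to two weeks off drug as on-treatment would be a debatable trade. That argues for leaving the PedsQL on-treatment cut-off alone.

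**Conclusion.** On a literal reading of Table 9, a palatability form from an EOT or premature-discontinuation visit on End Day 3 or later enters no summary row, and the Final Treatment Visit entry becomes the Week 2 answer where one exists. This is a limited but real defect in the summary of a named secondary endpoint. It assumes that the Table 9 rows are the visits tabulated under SAP 10.4.2.

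Three stronger readings are tempting, and the documents do not support them.

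- **A stated loss.** If visits scattered normally around the last dose with an SD of 1.5, 2 or 3 days, 1 − Φ(2.5/SD) would put 4.8%, 10.6% or 20.2% of them on End Day 3 or later: about 4, 9 or 16 of the 81 planned Part 2 children. Those SDs are pure assumption. The number affected is unknown.
- **A bias towards acceptance.** One might infer that the lost forms come mainly from children who stopped because they disliked the product. A loss spread over all 81 would fall mostly on completers with ordinary scheduling delay, which has no evident direction. The only discontinuation figure in the documents is for adults (Protocol Table 4: 8 of 2,265 stopped for an adverse event, 0.4%, or about 0.3 of 81). It may not carry over to granules.
- **General relabelling of PedsQL.** This happens only when no later post-treatment form exists; otherwise the late form is simply unused. PedsQL is not a listed secondary endpoint.

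**What to change.** **Palatability.** In SAP Table 9, assign a form collected at the EOT or treatment-period premature-discontinuation CRF visit to that visit and to the Final Treatment Visit, up to about End Day 14, in place of End Day ≤ 2. That limit matches the 14 days past nominal already printed in the table. Add a matching exception for palatability to the Final Treatment Value definition in SAP 6.1.2.

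**PedsQL.** Keep the 2-day rule for on-treatment values. Add a note to Table 8 that forms from the EOT or treatment-period discontinuation visit cannot supply the Post-Treatment Week 12 or Final Post-Treatment value.

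**All other data.** Leave the rule for HCV RNA, laboratory and vital-sign data unchanged. Protocol 5.1.2 and 5.4.1 word the early-stop visit timing differently and should be reconciled.

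**Cost.** Table-note wording and a small programming change, with no change to visits or data collection. The downside is up to two weeks' recall for a few palatability forms. A late EOT PedsQL score would appear in no windowed summary, so the number of such forms should be reported.
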